5.5.4. Endothelial biomarkers

vWF antigen levels and activity and E-Selectin levels will be assessed by commercially available enzyme linked immunoassays. EDTA- and citrate-anticoagulated blood samples will be centrifuged at 2000g for 15 minutes at 4 degrees Celsius and supernatant plasma will be transferred to aliquots of approximately 500µl each. These aliquots will be frozen and stored until batch analysis.

5.5.5. Differential blood counts

Differential blood counts will be performed at the central laboratory of the General Hospital of Vienna.

5.5.6. Blood Chemistry

Blood chemistry will be performed at the central laboratory of the General Hospital of Vienna before infusion of any trial drugs and 24 hours after infusion of LPS.

5.5.7 Global coagulation assays

Global coagulation assays will be performed at the central laboratory of the General Hospital of Vienna.

5.5.8. Circulating endothelial cells

Circulating endothelial cells will be assessed by flowcytometric analysis as previously described³⁶. 1ml of freshly drawn EDTA-anticoagulated blood will be first mixed with 10ml of FACS lysing solution (10x, diluted 1:10) according to the manufacturers instructions. The white cells will then be blocked with 20µl of specific Fc-receptor antibodies (Octagam) and 200µl of mouse serum (Sigma, Gillingham, UK) for a minimum of 20min at room temperature. Next, the cells will be incubated with fluorochrome-labelled monoclonal anti-human mouse antibodies, namely FITC-CD45, PE-CD146 and PE-Cy5-CD34 (Becton Dickinson, Oxford, UK) for 20 min at room temperature, washed with cell buffer solution [PBS + bovine serum albumin (BSA) 1% + sodium azide 0.05%] and centrifuged at 500g to repellet the cells. The cells will be fixed with 200µl of 2% paraformaldehyde for 20min at 4°C and made up to a final volume of 1ml with cell buffer solution ready for analysis. Each sample will be analysed in a 3-colour FACScan flow cytometer (Becton Dickinson, Oxford, UK). Cells will be plotted according to forward scatter and side scatter profiles (a measure of size and granularity of an event, respectively) and gated to include only mononuclear cell events and excluding cell doublets, platelets, dead cells/debris, microparticles and high side scatter events (e.g. dead cells and polynuclear cells have higher side scatter). A second gate will be used to include only those cells negative for CD45 (FITC) (CD45 is a pan-leukocyte marker, and a 'dump' channel will be constructed to exclude all CD45 positive cells including CD45dim cells as included in these are endothelial progenitor cells) and are low to medium side

scatter singlets. A third gate will be used to analyse cells doubly positive for CD146 (PE) and CD34 (PE-Cy 5) expression, and only high intensity doubly fluorescent cells (i.e. CD146+++/CD34++++) will be defined as CECs. The sample will be analysed for a minimum of 500,000 mononuclear cellular events and a pre-set time period, corresponding to a known volume of sample (predetermined from previous validation studies, data not shown). Fluorochrome-matched isotype controls (FITC-IgG1, PE- IgG1, PE-Cy5- IgG1; Becton Dickinson, Oxford, UK) as well as non-stained samples will be used to set the appropriate gate parameters and served as negative controls.

5.5.9. LPS quantification

Blood for LPS quantification will be collected in citrate tubes and put on ice. Within 30 minutes from collection, samples will be centrifuged at 4°C and 2000 g for 10 minutes and resulting plasma transferred into 3 aliquots of approximately 500 µL each. All aliquots will be snap frozen at -20°C and later stored at -80°C until analysis. LPS will be measured at the Department of Pharmaceutical Biosciences, Uppsala University, Sweden, by means of a chromogenic limulus amoebocyte lysate assay. Optionally, a second method of LPS quantification (Haemotox rFC, Haemochrom Diagnostica, Germany) might be used and results compared with the LAL assay.

6. Trial Materials

6.1. Trial Products

LPS: US Standard Reference Endotoxin, CC-RE Lot 2, vialled by

MARP/NCI

Manufacturer: FROC 2ng/ml

Dose: 2ng/kg administered at 0 min as an i.v. bolus over 1-2 min

Defibrotide: Defitelio, 80mg/ml, Ampullae of 2,5ml

Manufacturer: Jazz Pharmaceuticals

Dose: 6.25mg/kg bodyweight as a continuous infusion over 2 hours

Physiologic Saline: Isotone Kochsalz-Lösung 0,9% Braun

Manufacturer: Braun

Dose: 100ml/h for six hours

Paracetamol: Paracetamol Genericon

Manufacturer: Genericon Pharma

Dose: Paracetamol 500mg p.o. on demand

6.2. Packaging and Labeling of trial products

Not applicable.

6.3. Storage and Drug Accountability of Trial Product(s)

All trial products should be stored in a secure place.

Defitelio should be stored at room temperature. After dissolution it should be kept refrigerated and used within 24 hours according to the manufacturer.

LPS should be kept refrigerated at 4-8 °C.

Saline and paracetamol should be stored at room temperature.

A record of all supplies dispatched to the investigator will be maintained by the Monitor.

The investigator will keep accurate records of all used and unused supplies. No trial products may be dispensed to any person except to the subjects en-rolled in the trial.

6.4. Randomization and Blinding

All screened subjects will receive a screening number. This number will be the identifier of each subject within the trial. A subject identification list, which links the screening numbers with the names and birth dates of each participating subject will be kept in the trial master file and in the “study maker” (the computer system of the Department of Clinical Pharmacology). In future publications we will only refer to numbers of subjects, but not to names or birth dates.

A physician not performing other tasks in the trial will observe the subjects.

Block randomization will be performed using an open access randomization generator (www.randomization.com).

Three sets of sealed code/label with the randomization number containing information about the treatment allocation (LPS or placebo group, DF or placebo period) for the particular subject will be prepared for each subject.

The code for a particular subject can be broken in a medical emergency if knowing the identity of the treatment allocation would influence treatment of the subject. Whenever a code is broken, the person breaking the code must record the time, date and reason as well as their initials in the source documents.

All codes (whether broken or not) must be kept throughout the trial period.

Breaking of the code, however, does not necessarily mean that the plasma obtained from the subject is not eligible for analyses, which can still be performed in a blinded fashion.

6.5. Potential inconveniences and risks for the subjects

6.5.1. Defibrotide

Defibrotide is approved by the FDA and the EMA for treatment of the sinusoidal obstruction syndrome (also called veno-occlusive disease) after hematopoietic stem cell transplantation or chemotherapy. Only few studies exist investigating the effects of DF in healthy volunteers^{7,37}. No serious or severe adverse events were reported in these trials.

The summary of product characteristics suggest that the most important adverse events of DF are hemorrhage, hypotension and coagulopathy²⁶. Of note, compared to a historical control group these side effects did not occur more frequently in the DF group indicating that these side effects may be due to the selection of patients, who were all thrombopenic critically ill patients³⁸.

No hypersensitivities or anaphylactic reaction were reported in the marketing trials^{20,38}. However, in previously marketed defibrotide products hypersensitivities and anaphylactic reactions have been reported²⁶. Thus, all participant will be made aware of that risk and special attention will be paid to potential anaphylactic reactions. We expect minor anti-coagulatory effects after infusion of DF. However, studies suggest that the effects of DF are only short termed and DF should be eliminated completely within 24 hours. All subjects will be made aware of an increased bleeding risk on the treatment days.

6.5.2. LPS

2-4ng/kg bodyweight are safe doses, which have already been used in clinical trials³⁰ and at the investigational site in over 1000 subjects. LPS produces flu-like symptoms consisting of fever, chills, myalgias, arthralgias, nausea and headache which are most

prominent 2-3h following endotoxin, and begin to resolve after 6 hours. Overall, infusion of endotoxin is generally well tolerated and trial subjects are virtually free of symptoms after 8 hrs.

6.5.3. Paracetamol

At therapeutic dosages (0.5 to 1g orally bid or tid) paracetamol is usually well tolerated and no common adverse effect has been established. Rarely allergic skin reactions may be seen. Chronic abuse or overdose can lead to disturbances in kidney and liver function.

6.5.4. Blood sampling

A total amount of approx. 500ml of blood will be collected during the duration of 8 weeks. This is about the volume of one blood donation. Between the two study periods a washout period of 6 weeks will apply. Thus, the blood volume should not impose any dangers on subjects. Care will be taken to avoid formation of subcutaneous haematomas after venipunctures.

6.5.5. Risk/benefit assessment

Endotoxin infusion in humans is a safe standard model, which induces a systemic inflammatory response and which has been safely used in more than 1000 volunteers at our institution. This inflammatory response is limited in duration and severity and can be used with restrictions as a model for the early phase of human sepsis.

Defibrotide has been used in clinical trials and clinical practice for over 30 years. Although many *in vitro* and animal studies have been published and effects in patients with SOS³⁸, with atherosclerosis obliterans³⁹ or peripheral arterial occlusive disease⁴⁰,

as a prophylaxis against deep venous thrombosis after surgery⁹, and other diseases have been investigated, the mode of action is still not entirely understood. However, in all those studies the use of DF was safe and no serious or severe AEs occurred.

The aim of this trial is to better define the pharmacodynamic effects of DF in a well established model of acute, transient inflammation in healthy volunteers. Furthermore, this trial will allow comparison of DF and other drugs that have already been investigated in this model and will help to generate further hypotheses about new indications of DF. The main risk of DF is a potential allergic reaction or bleeding episodes. However, the anti-coagulatory effects of DF will be closely monitored and strong anticoagulatory effects are not expected. Allergic reactions are rare, but must be considered a potential risk.

In conclusion we consider the benefits to clearly outweigh the risks in this study.

6.6. Safety precautions

Throughout the trial-period the subjects will be observed by a physician. In addition, a physician with experience in emergency medicine will be at the unit during the first eight hours. The clinical trial center is equipped with monitoring facilities comparable to an intensive care unit.

The subjects will be supine with their chest tilted up throughout the trial period and their vital parameters monitored (ECG, heart rate and oxygen saturation continuously; blood pressure at 20 min intervals). Oral temperature will be checked every hour during the first 6 hours.

Frequent blood cell counts and monitoring of platelet function will be done.

Although our experience with more than 1000 LPS challenges showed no severe untoward effects, all adverse events will be managed by adequate medical measures according to standard practice. Evaluation of the safety parameters will be performed for each trial subject, which includes checks of C-reactive protein, GPT-levels blood cell count 24 hours after the endotoxin bolus.

7. Concomitant Illness and Medication

Concomitant illness: any illness that is present at the start of the trial

Concomitant medication: any medication other than the trial product that is taken during the trial, including screening and run-in periods

7.1. Concomitant Medication during the Trial

No concomitant medication is planned.

7.2. Precautions/Overdosage

As all drugs will be administered at the study site by a physician and controlled by an independent staff member according to SOP, no overdose are described in the Investigator's Brochure.

8. Adverse Events

8.1. Definitions

8.1.1. Adverse Events

An AE is any undesirable medical event occurring to a subject in a clinical trial, whether or not considered related to the trial product(s). This includes events not seen at baseline or worsened if present at baseline. The following should not be re-corded as AEs, if recorded at screening (on Screening Form or CRF):

Pre-planned procedure, unless the condition for which the procedure was planned has worsened since baseline

Pre-existing conditions found as a result of screening procedures.

8.1.2. Clinical Laboratory Adverse Events

A clinical laboratory AE is any clinical laboratory abnormality that suggests a disease and/or organ toxicity and is of a severity which requires active management (i.e. changes of dose, discontinuation of drug, more frequent follow-up or diagnostic investigation).

8.1.3. Serious Adverse Events (SAE)

An SAE is any adverse drug experience that at any dose results in any of the following outcomes:

- death
- a life-threatening* experience
- in-patient hospitalization or prolongation of existing hospitalization
- a persistent or significant disability/incapacity
- a congenital anomaly/birth defect.

Important medical events that may not result in death, be life-threatening, or require hospitalization may be considered a serious adverse drug experience when, based upon appropriate medical judgment, they may jeopardize the health of the subject or patient and may require medical or surgical intervention to prevent one of the outcomes listed

in this definition.

*The term life-threatening in the definition of serious adverse event refers to an event in which the subject was at risk of death at the time of the event. It does not refer to an event, which hypothetically might have caused death if it was more severe.

8.1.4. Non-Serious Adverse Event

A non-serious adverse event is any AE, which does not fulfill the definition of an SAE.

8.1.5. Severity Assessment Definitions

Mild: transient symptoms, no interference with the subject's daily activities.

Moderate: marked symptoms, moderate interference with the subject's daily activities.

Severe: considerable interference with the subject's daily activities unacceptable.

8.1.6. Relationship to Trial Drug Assessment Definitions:

Probably: Good reasons and sufficient documentation to assume a causal relationship

Possible: A causal relationship is conceivable and cannot be dismissed

Unlikely: The event is most likely related to an aetiology other than the trial treatment

Impossible to assess: Causality is not assessable, e.g. because of insufficient evidence, conflicting data or poor documentation.

8.1.7. Outcome Categories and Definitions:

Recovered

Stabilized: An AE is stabilized when, according to the Investigator, the subject is in a clinically stable condition. This term should only be used for chronic conditions and for a given subject only when he/she has completed the protocol

Recovered with sequelae: As a result of the SAE, the subject suffered persistent and significant disability/incapacity (e.g. became blind, deaf, paralyzed). Any AE re-covered with sequelae should be rated as an SAE.

Not yet recovered

Died

Unknown.

8.2. Collection, Recording and Reporting of Adverse Events

All events meeting the definition of an adverse event must be collected and reported from the first trial-related activity after the subject signs the informed consent and until the end of the protocol required post-treatment follow-up period.

At each contact to the site (visit or telephone, excluding safety visits, where the subject is not seeing the Investigator or his staff (e.g. visits to the laboratory)), the subject must be asked about adverse events. All adverse events, either observed by the Investigator or reported by the subject, must be recorded by the Investigator and evaluated.

The subjects will be asked a general question "How are you?" as well as a specific question "Have you experienced any problems since the last contact?"

The Investigator should record the diagnosis, if available. If no diagnosis is available the Investigator should record each sign and symptom as individual Adverse Events.

All adverse events must be recorded by the Investigator on the standard Adverse Event Form. One single Adverse Event Form/line must be used per adverse event from start to resolution. For serious adverse events, the Serious Adverse Event Supplementary pages 1-4 must also be completed.

The Investigator must inform the Health Authorities and IRBs/IECs in accordance with the local requirements in force and ICH guideline for GCP. The Monitor must be informed accordingly.

8.3. Follow-up of Adverse Events

During and following a subject's participation in a clinical trial, the Investigator/institution will ensure that adequate medical care is provided to the subject for any adverse events, including clinically significant laboratory values related to the trial. The investigator/institution will inform the subject when medical care is needed for adverse event(s) of which the investigator becomes aware. The active post-treatment follow-up period will end with the post-trial examination.

All adverse events classified as serious or severe or possibly/probably related to the trial product must be followed until the subject has recovered, stabilized, recovered with sequelae or died, and until all queries have been resolved.

All other adverse events must be followed until the subject has recovered or stabilized or until the end of the protocol required post-treatment follow-up whichever comes first, and until all adverse event related queries for the subject have been re-solved.

8.4. Case record forms

A case record form will be completed for each subject. The entries will be checked by trained personnel and any errors or inconsistencies will be corrected immediately. CRFs will be completed by trained personnel at the trial site.

8.5. Rules for completing CRFs

Print legibly using a ball-point pen. Ensure that all relevant questions are answered and that no empty data blocks exist.

If a test/assessment is not done and will not be available, indicate this by writing „N/D“ (Not done) in the respective answer field in the CRF. If the question is irrelevant (e.g. is not applicable) indicate this by writing „N/A“ (Not applicable) in the respective answer field.

The investigator or investigator's authorized staff must ensure that all information derived from source documents should be consistent with the source information. By signing the affirmation statement, the investigator confirms that the information is complete and correct.

8.6. Correction of CRFs

Corrections to the data on the CRFs must only be made by drawing a straight line through the incorrect data and by writing the correct value next to data that has been crossed out. Each correction must be initialed and dated and explained (if necessary) by the Investigator or the Investigator's authorized staff. If corrections are made by the Investigator's authorized staff after the date of the investigator's signature on the affirmation statement, the statement must be signed and dated again by the investigator.

Corrections necessary after the CRFs have been removed from the Investigator's site must be documented on a Query Resolution Form (QRF). If the affirmation statement for the subject has not been signed, corrections must be approved by the Investigators or her/his authorized staff. If the affirmation statement for the subject has been signed, only the investigator can approve the correction.

8.7. CRF Flow

Paper CRFs will be used and stored at the trial side. Laboratory report of pre-and post-trial screening examinations will be attached as copies to the CRFs, in case of clinically relevant deviations from normal this will be protocolled in the CRF. The Investigator or

another authorized physician will sign analysis results (e.g. laboratory, ECG, etc.) as soon as they are available to verify that the results are reviewed.

9. Monitoring procedures

During the course of the trial, the Monitor will visit the investigational site approximately two times during each part and must be available for discussions by telephone. The purpose of these visits is to ensure that the CRFs are completed correctly, the protocol is adhered to, to monitor drug accountability, and to collect completed pages of the CRFs.

The Monitor must be given direct access to source documents (original documents, data and records). Direct access includes permission to examine, analyze, verify and reproduce any record(s) and report(s) that are important to evaluation of the clinical trial. Source data will be available for all data in the CRFs, including all laboratory results.

The Monitor will ensure that the CRFs are collected.

10. Data Management

The subjects will be identified by subject number, initials, site, and trial identification number. Subject initials will be retained in the database only during the period of trial data processing. Upon completion of the Integrated Clinical Trial Report, subject initials will be deleted or encrypted to ensure subject confidentiality.

Electronic data transfer of any CRF or subject related data must be approved by the responsible Data Management Unit(s). In cases where data is transferred via non-secure electronic networks, data must be encrypted at source.

11. Statistical Considerations

11.1. Sample Size Calculation

The sample size calculation is based on the experience with prior trials using anti-coagulants in the human endotoxemia model. Ten to 15 subjects in each group were sufficient to detect significant differences in the primary outcome parameter (F1+2 levels) between treatment groups in a parallel-group study^{14,23,24}. Currently, we do not have a good estimate for the size of effect of defibrotide in the same model. In a prior LPS trial F1+2 levels of approximately 819 ± 173 (Standard deviation) pmol/ml were measured ⁴¹. This corresponds to an approximate 6fold increase in F1+2 levels and was similar in other endotoxemia trials⁴². The median intraindividual coefficient of variation was 15% in a recent study, the mean was 25%³². Thus, a sample size of 16 volunteers will be sufficient to detect a 25% decrease in the defibrotide period.

The placebo group consisting of four healthy volunteers will be an additional control group, which will also allow to assess the effects of DF in healthy volunteers without LPS. However, this analysis is exploratory and no sample size calculation for this group is performed.

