3.1. Flow Chart

3.2. Trial design and rationale

Before initiation of the trial we will investigate the effects of DF on thrombelastometry ex vivo. In this part blood samples will be drawn from a minimum of eight healthy volunteers and after *ex-vivo* spiking of blood samples with increasing doses of DF thrombelastometry will be performed. The effects of activators (i.e. recombinant tissue factor) on DF in thrombelastometry will be investigated. The number of participants may be increased to 16 after analysis of the results of the first eight subjects.

This trial is designed as a randomized, double blind, crossover trial in 20 healthy volunteers. Sixteen healthy volunteers will be randomly assigned to receive LPS, whereas four healthy volunteers will be randomly assigned to the placebo group. In each group two treatment periods will be performed. In one treatment period all subjects will be treated with DF. In the other treatment period all subjects will be treated with placebo. A washout period of 6 weeks will be planned between both treatment periods to reduce the risk of any carry-over effects. Whether a subject starts with the placebo or the DF period will also be randomized.

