3.3.3 Timing

For this trial we chose to infuse 6.25mg/kg bodyweight over a period of two hours, which is the approved dose of this drug. The LPS bolus will be infused 1h after the start of the defibrotide infusion. We chose this dosing regimen based on the T_{max} of DF of two hours, the $T_{1/2}$ of 0.7 hours and the effects of LPS with a maximum approximately four hours after infusion of the bolus.

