11.2. Methods

Two-sided tests and a 5% critical value will be used throughout the trial. Test procedures to reduce multiple testing will be applied. Refer to the detailed, separate statistical analysis plan for further information.

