11.2.1 Efficacy Analysis

The efficacy analysis will compare changes in the primary and secondary efficacy endpoints described above between the placebo and the DF periods.

The repeated measures analysis of variance (ANOVA) will be used for analysis of treatment and period effects (treatment=independent factor, period=independent factor, outcome variable=dependent factor). When significant, post hoc comparisons will be performed with nonparametric tests for reasons of robustness: The Friedman ANOVA and the Wilcoxon test for post hoc comparisons will be used.

Furthermore, graphs showing the time profiles at the individual subject and group mean levels will be presented.

Multiple parameters will be tested. However, to reduce the number of tests a stepwise statistical analysis plan will be applied. Moreover, this study is of exploratory nature and correcting for multiple testing is therefore not necessary.

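### In the four no-LPS controls the post hoc Wilcoxon test cannot reach the 5% level (smallest exact two-sided p is 0.125), so a non-significant post hoc result there says nothing about DF

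*Combined protocol and SAP*

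**What the plan says.** Four of the 20 volunteers receive placebo in place of LPS. Section 3.2 makes them a crossover group like the other 16: "In each group two treatment periods will be performed", one with DF and one with placebo. Section 11.1 gives their purpose, "The placebo group consisting of four healthy volunteers will be an additional control group, which will also allow to assess the effects of DF" without LPS, and then qualifies it: "However, this analysis is exploratory and no sample size calculation for this group is performed".

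On testing, section 11.2 states: "Two-sided tests and a 5% critical value will be used throughout the trial". Section 11.2.1 names the first analysis: "The repeated measures analysis of variance (ANOVA) will be used for analysis of treatment and period effects". It then adds: "When significant, post hoc comparisons will be performed with nonparametric tests for reasons of robustness", and "The Friedman ANOVA and the Wilcoxon test for post hoc comparisons will be used". Graphs of individual and mean time profiles are also planned. No test is assigned specifically to the four controls, and section 11.2 refers to a separate SAP for details.

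On sampling, section 3.3.3 says: "The LPS bolus will be infused 1h after the start of the defibrotide infusion". Table 1 in section 5.4 lists a 0h sample, defined as taken before the LPS injection, for the coagulation, fibrinolysis, endothelial and inflammatory markers. The visit descriptions in 5.1.3 and 5.1.5 list baseline and 1, 2, 4, 6 and 24 hours, with no 0h draw.

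**The concern.** Taken as written, the rules of section 11.2.1 apply to every DF-versus-placebo comparison, including the one in the four controls. The confirming step there is a test with too few pairs to reach the level set for it, whatever the data show. The protocol chose the nonparametric step for robustness, yet in this group it can only ever return a non-significant result.

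What is at stake is how the result is read. These four subjects are the plan's named source of information on DF without LPS. A report that the post hoc test was not significant could pass for evidence that DF does nothing in unstimulated volunteers. The plan gives no warning against that reading, and names no estimate or interval to report for the group instead.

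**Working it through.** **Inputs.** Four controls with one DF and one placebo period each (3.2, 11.1); two-sided 5% level (11.2); ANOVA first, Wilcoxon and Friedman post hoc (11.2.1); intraindividual CV of 15% (median) and 25% (mean) and a target decrease of 25% (11.1). The CVs come from an LPS study. Applying them to subjects without LPS is an assumption, so both are carried through.

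**The plan's own figure.** Section 11.1 gives 16 subjects for a 25% decrease and states no power. Assuming 80% power and a CV of 25%, n = (1.960 + 0.842)² × 2 × (0.25/0.25)² = 15.7, so 16. The figure is reproduced. It concerns the LPS group only; no figure is given for the four controls.

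**Floor of the post hoc test.** Under the null hypothesis, four paired differences have 2⁴ = 16 equally likely sign patterns. The most extreme result is all four in one direction, so the smallest exact two-sided p is 2/16 = 0.125. Other versions of the test:

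- Normal approximation for untied data: 0.068, or 0.100 with continuity correction.
- Exact Friedman test on the two periods: 0.125. Its chi-square approximation can give 0.0455, which is an artefact of using the approximation with four blocks.
- Exact Wilcoxon with five pairs: 2/32 = 0.0625. With six: 2/64 = 0.031. Six is the smallest number at which it can fall below 0.05.

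**The ANOVA has no such floor.** Take illustrative differences (chosen here, not from the documents) of −0.20, −0.25, −0.30 and −0.22. Their mean is −0.2425 and their SD 0.0435, so t = −0.2425/(0.0435/√4) = −11.15 on 3 df and p = 0.0015. The exact Wilcoxon p for the same data is 0.125.

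**Power of an ANOVA-type test with four subjects.** The SD of a paired difference is CV × √2, and the noncentrality is effect × √4/SD. For a 25% effect:

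| CV | SD of difference | Noncentrality | Power, 3 df | Power, 2 df (period fitted) |
|---|---|---|---|---|
| 15% | 0.212 | 2.36 | 37% | 28% |
| 25% | 0.354 | 1.41 | 17% | 14% |

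For a 50% effect with 3 df, power is 87% (CV 15%) or 49% (CV 25%).

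**Precision of an estimate.** On the log scale the SD of a paired difference is √(2 ln(1 + CV²)): 0.211 for a CV of 15% and 0.348 for 25%. The 95% interval for the DF/placebo ratio runs from the estimate divided by a factor to the estimate times that factor, where factor = exp(t × SD/√n). Period is fitted and sequences are taken as balanced:

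| Data | t | CV 15% | CV 25% |
|---|---|---|---|
| Four controls, 2 df | 4.303 | exp(0.454) = 1.57 | exp(0.749) = 2.12 |
| 0h sample, 20 subjects, 18 df | 2.101 | exp(0.099) = 1.10 | exp(0.164) = 1.18 |

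The 0h row is possible because DF or placebo has then been running for one hour and nobody has yet received LPS, so all 20 subjects contribute a comparison without LPS. Adjusting for the Pre value would use one more degree of freedom; that is not included here.

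**The case against.** The strongest reply is that the Wilcoxon test is not the primary test. Section 11.2.1 puts the repeated measures ANOVA first and reaches the nonparametric tests only if it is significant. A reader might infer from the 0.125 floor that the whole comparison of DF without LPS is bound to be negative, or that its power is zero. The documents do not support that: the ANOVA can reject with four subjects, and for a large effect with small variability its power is substantial. The floor applies to the confirming step alone.

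Second, section 11.1 openly calls this analysis exploratory and unsized. That stands and limits the consequence. It excuses low power, but it is no reason to name a test that cannot reject under any data.

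Third, no test is tied to this group by name, and the separate SAP was not available. It may treat the controls differently. The point therefore rests on reading the general rules of 11.2 and 11.2.1 as covering them.

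Fourth, individual profiles are already planned, so that part of a remedy exists. A reader might also infer that the 0h sample goes unused. That is not shown: nothing excludes it from the repeated measures analysis or the time profiles. What the protocol lacks is a named pre-LPS contrast that pools all 20 subjects.

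Finally, 0h is no substitute for the controls. Section 3.3.3 gives a two-hour infusion and a Tmax of two hours, so 0h is midway through the infusion and says nothing about later times, which only the controls cover without LPS.

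**Conclusion.** The point holds for the post hoc step. With four pairs the exact Wilcoxon test cannot go below p = 0.125, and an exact two-period Friedman test has the same floor. This needs no assumption about variance or effect size. In this group the post hoc step can never confirm a significant ANOVA, and a non-significant post hoc result is uninformative.

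The comparison as a whole is weak but not predetermined: about 14% to 37% power for a 25% effect. That range, like the interval factors, rests on carrying the LPS-derived CVs over to unstimulated subjects. Since the protocol labels the analysis exploratory, this is a cheap improvement that should be made. It does not affect the primary comparison in the 16 LPS subjects.

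**What to change.** 1. In 11.1 and 11.2, state that the post hoc nonparametric tests are not applied to the four controls, and that a non-significant result in this group is not evidence that DF has no effect.
2. For this group, report DF/placebo ratios with 95% confidence intervals beside the individual profiles already planned.
3. Pre-specify a DF-versus-placebo contrast on the 0h sample in all 20 subjects, on the log scale, adjusted for the Pre value and with period in the model. Describe it as a complement to the controls' later time points.
4. Reconcile 5.1.3 and 5.1.5, which omit the 0h draw, with Table 1, which lists it. Item 3 depends on that sample being taken.
5. If the separate SAP already sets other rules for the controls, refer to them in 11.1 and 11.2.

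The cost is some wording and one extra model, with no added subjects and no samples beyond Table 1. The limitation to state with the 0h result is that it reflects only the first half of the infusion.
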